6.4.8 Concomitant medication

6.4.8.1 Permitted Medications

The following rescue medications will be provided. These medications are considered standard of care and will be provided approximately 2 weeks before the start of the pollen season (May 2014) and throughout the pollen season:

- Antihistamine (e.g. desloratidine).
- Nasal corticosteroid (e.g. fluticasone propionate aqueous nasal spray).
- Ophthalmic antihistamine (e.g. olopatadine eye drops).

Use of the following rescue medications will be provided by the study only after participants are evaluated by the investigator. Evaluations may occur by phone contact or clinic visit.

- Oral corticosteroid (e.g. prednisolone).
- Short-acting beta-agonists (e.g. salbuterol).
- Inhaled corticosteroids (e.g. fluticasone).
- Combination long-acting beta-agonists or steroids (e.g. salmeterol/fluticasone).

Refer to **Appendix 7** for required medication washout periods prior to screening, nasal challenges and biopsies (V-1, V0b, V5, and V7).

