6.5.7 Nasal allergen challenge

Nasal allergen challenge is performed with Aquagen SQ (ALK 225) Timothy grass pollen, *Phleum pratense*, ALK-Abelló freeze dried extract (Cat. no. 1001862, ALK-Abello, Denmark). Fresh extracts will be reconstituted in albumin-based diluent (ALK-Abello) on a weekly basis at a concentration of 100,000 SQ-U / 30,000 BU per ml. On a daily basis, a fresh dilution of 5,000 BU/ml in normal saline will be prepared from the stock solution. This solution will be added to a nasal applicator device (Bidose, Aptar Pharma/Pfeiffer, Germany), designed to spray a standard volume (100µL) with each metered dose pump application. A single spray will be applied to each nostril, giving a total allergen dose of 1,000 BU. Following the nasal challenge the EPR will be measured using the TNSS (**Appendix 6**). A score $\geq 7/12$ points after 5 minutes during screening will be interpreted as a positive response and patients will be included in the study. If during screening the proportion of patients not being included in the study because of this inclusion criterion exceeds 20% the cut-off for inclusion will be lowered to ≥ 5 points.

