6.5.9 Intradermal skin tests

Intradermal skin tests are performed by injecting 0.02ml of allergen diluted in albumin-based diluent into the skin of the outer surface of the forearms. 1 BU (0.02ml of 50

BU/ml) will be injected into the right and the left forearm. A negative control injection of 0.02ml of normal saline will be injected on the outer surface of the wrist on the right.

Skin responses are defined as follows:

Response	Skin Allergen Challenge
Early Phase Response (EPR)	Measured 15 Minutes after Allergen Challenge \pm 5 min
Late Phase Response (LPR)	Measured 8 Hours after Allergen Challenge \pm 1 hour

In pollen sensitized individuals, allergen skin injection provokes a local wheal and flare skin response, peaking at about 15 minutes. This is recorded in comparison with the negative control (saline) injection. In sensitized, allergic individuals, following resolution of the early wheal and flare response, there is a gradual onset mild swelling and redness over a larger area around the site of the injection – the LPR. This response is measured at 8 hours after injection using a pencil-friction technique to map out the extent of skin swelling. Volunteers may experience mild to moderate itchiness or local discomfort at the sites of intradermal injections and skin pricks with allergen. The symptoms are not bothersome and treatment with oral antihistamines is always available and is effective although almost never required. Systemic reactions including anaphylaxis after skin tests with standardized aeroallergen extracts are a theoretical risk but exceedingly rare. However, a physician is always present and drugs and equipment for treatment of anaphylactic reactions available.

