Around 5 months after begin of AIT/placebo and during the pollen season participants will come to the hospital for 1.5 hours. During this visit the following will be undertaken (see also **Table 4**):

- A period of 15 minutes acclimatization to hospital environment and relative inactivity.
- Participants will mark questionnaires (**Appendix 3-5**) corresponding to symptoms and rescue medication use during the current pollen season.
- Furthermore the volunteers will undergo the same procedures as in Visit 0b, plus questionnaires and with the exception of the intradermal skin test and nasal challenge.

Table 4: Time line procedures at Visit 5

Time (hr:min)		Procedure
00:00	Arrival	
00:05	Blood	Blood sample (200ml)
00:15	Pre-lavage	GE VAS; mRQLQ; SMS, secretion collection
00:20	Pre-lavage	Nasal brushing
00:25	Nasal-lavage	
00:55	Post-lavage	Secretion collection

		Nasal biopsy
--	--	--------------

GE VAS; Global Evaluation visual analogue scale

mRQLQ; mini Rhinitis Quality of Life Questionnaires

SMS; symptom medication score

Visit 6:

After 6 months of treatment and shortly after the pollen season patients will mark a retrospective GE VAS (scale 0-100 mm; **Appendix 1**), the mRQLQ (**Appendix 3**) and complete a retrospective GE chart (**Appendix 2**) documenting the overall severity of their hay fever symptoms during the previous pollen season. Also a nasal allergen challenge with 5.000 BU/ml Timothy grass pollen allergen will be undertaken. We will record the Peak Flow as well as the response to challenge for one hour at 5, 15, 30 and 60 min with TNSS + VAS and PNIF.

Time (hr:min)		Procedure
-00:15	Arrival	TNSS+VAS; GE VAS, mRQLQ, GE, PNIF; Peak Flow
00:00	Nasal Challenge	5,000 BU/ml Timothy grass pollen allergen
00:05	Early Nasal response	TNSS + VAS; PNIF
00:15	Early Nasal response	TNSS + VAS; PNIF
00:30	Early Nasal response	TNSS + VAS; PNIF
01:00	Early Nasal response	TNSS + VAS; PNIF; PeakFlow

Visit 7:

After 12 months on treatment volunteers will attend the allergy unit for a period of 2 hours in the morning and 1 hour during the evening (3 hours). During this visit the same procedures as described at Visit 0b plus a blood sample of 200 ml will be undertaken (see also **Table 2**).

Non-atopic Participants:

Scheduled Visits (screening (Visit -1), one time point assessment (Visit 1):

Screening Visit – September 1st to November 30th, 2014.

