Appendix 8: Medication washout periods prior to visit-1, 0, 5, and 7.

Medication Washout Periods	
Medications	Time
Inhaled β-agonists	
Short acting (e.g., Salbutamol, Ventolin, Salamol Easi-Breathe, Terbutaline, Bricanyl)	6 hours
Long acting (e.g., Salmeterol, Serevent, Formoterol, Foradil, Oxis)	2 days
Oral β-agonists	
Conventional release (e.g., Salbutamol, Ventolin)	12 hours
Modified release (e.g., Bricanyl)	2 days
Cromolyn drugs (e.g., Intal, Tilade)	7 days
Leukotriene modifiers (e.g., Montelukast, Singulair, Zafirlukast, Accolate)	3 days
Inhaled corticosteroids (e.g., Beclomethasone, AeroBec, Asmabec Clickhaler, Beclanzone Easi-Breathe, Becodisks, Qvar, Budesonide, Pulmicort, Symbicort, Flixotide, Seretide, Asmanex)	14 days
Oral steroid (e.g., prednisone)	14 days
Theophylline product	14 days
Short-acting preparation (e.g., Nuelin SA, Slo-Phyllin, Aminophylline)	24 hours
Long-acting preparation (e.g., Uniphyllin Continus, Phyllocintin Continus)	2 days
Rhinitis Medications	Time
Sodium Cromoglicate (e.g., Rynacrom, Vividrin)	7 days
Antihistamines (e.g., Cetirizine, Desloratadine, Neoclaritin, Fexofenadine, Telfast, Levocetirizine, Xyzal, Loratadine, Chlorphenamine, Piriton, Atarax, Zaditen)	5 days
Decongestants (e.g. pseudoephedrine, phenylephrine)	3 days
Antihistamine-decongestant tablets/liquids (e.g., Zyrtec D, Claritin-D)	3. days
Nasal corticosteroids (e.g., Flixonase NS, Flixonase Nasules, Nasonex, Nasacort, Flonase, Nasonex, Beclomethasone, Beconase, Betnesol, Vista-Methasone, Budesonide, Rhinocort Aqua)	14 days
Médications (Prior to antigen nasal biopsy)	Time
Aspirin, NSAIDs, or other anti-platelet agents	2 days

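### Minor: Appendix 8 sets a 3-day washout for antihistamine-decongestant products but 5 days for antihistamines alone, ahead of the screening, baseline and primary challenges

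*Protocol*

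**What the plan says.** Protocol Appendix 8 is titled "Medication washout periods prior to visit-1, 0, 5, and 7". Three of its rhinitis rows matter here:

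- The row "Antihistamines (e.g., Cetirizine, Desloratadine, Neoclaritin, Fexofenadine, Telfast, Levocetirizine, Xyzal, Loratadine, Chlorphenamine, Piriton, Atarax, Zaditen" carries an interval of 5 days.
- The row "Decongestants (e.g. pseudoephedrine, phenylephrine" carries an interval of 3 days.
- The row "Antihistamine-decongestant tablets/liquids (e.g., Zyrtec D, Claritin-D" also carries an interval of 3 days, printed with a full stop between the number and the unit.

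No footnote explains the third value, no other section of the protocol does so, and the SAP has no washout rule.

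Protocol 6.4.8.1 makes the table binding, since it speaks of "required medication washout periods prior to screening, nasal challenges and biopsies (V-1, V0b, V5, and V7". It cites Appendix 7 for this, but Appendix 7 is the visual analogue scale used after the challenge. The washout table is Appendix 8.

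The challenges that the table protects carry weight. Under Protocol 6.5.7, a TNSS of at least 7 of 12 "after 5 minutes during screening will be interpreted as a positive response and patients will be included in the study". V0b supplies the baseline challenge, and Visit 7 supplies the primary endpoint (Protocol 6.1). V0b and Visit 7 also include the intradermal tests behind a secondary endpoint (Protocol 6.2.1).

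Visit 6 has a challenge too: "Also a nasal allergen challenge with 5.000 BU/ml Timothy grass pollen allergen will be undertaken" (Protocol 6.5.14). Protocol 6.5.15 repeats all Visit 7 procedures at Visits 8 and 9.

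**The concern.** The row's own name says that the product contains an antihistamine, yet its interval is the one given for decongestants alone. A participant who stops such a product 3 or 4 days before a challenge satisfies the row but breaches the interval that the same table sets for an antihistamine.

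The plan treats antihistamines as able to interfere with its allergen tests. It requires them to be stopped beforehand, and Protocol 6.5.9 says of skin-test symptoms that "treatment with oral antihistamines is always available and is effective". Residual drug could therefore blunt the TNSS at the challenges that decide eligibility, set the baseline and give the primary outcome. It could also blunt the skin responses at V0b and Visit 7.

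The visit list raises a related question. A challenge visit that is not named has no clearly stated washout, and Visit 6 comes shortly after a season in which participants were given antihistamines and nasal corticosteroids.

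**Working it through.** No sample-size or test calculation is involved. The check compares rows of one table, then compares the table's visit list with the visit schedule.

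**1. The interval.** Inputs, all from Appendix 8: antihistamine 5 days, decongestant 3 days, combination 3 days.

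- A product with two components needs the longer of the two washouts: max(5, 3) = 5 days.
- Printed value: 3 days.
- Shortfall: 5 − 3 = 2 days, which is 2/5 = 40% of the antihistamine interval.
- If the stray full stop hides a lost decimal digit, the value lies between 3.0 and 3.9, which is still below 5.

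**2. The visits.** Dates and procedures are from Protocol 6.5.14 and 6.5.15.

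| Visit | Nasal challenge | Named in Appendix 8 | Scheduled | Phase |
|---|---|---|---|---|
| -1 (screening) | yes | yes | Dec 2013 to Apr 2014 | before randomisation |
| 0b (baseline) | yes | yes | Jan to Apr 2014 | before the first tablet (Visit 1) |
| 5 | no (biopsy) | yes | May to Aug 2014 | blinded treatment |
| 6 | yes | no | Jul to Oct 2014 | blinded treatment |
| 7 (primary) | yes | yes | Jan to Apr 2015 | blinded treatment |
| 8 | yes | no | Jan to Mar 2016 | open |
| 9 | yes | no | Jan to Mar 2017 | open, after withdrawal |

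The 3-day row therefore applies to three challenges: screening, V0b and Visit 7. The blinded treatment phase contains two challenges, Visits 6 and 7, and the table names one of them. All three challenges it covers fall between December and April. Protocol 6.3.2 places peak symptoms from mid-May to mid-July.

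**3. Likely exposure.** The antihistamine tablet that the study supplies is exemplified by desloratadine, which the 5-day row names. No supplied rescue product is a combination (Protocol 6.4.8.1). Atopic participants with seasonal symptoms outside the grass season are excluded (Protocol 6.3.3). The exclusion for a current upper respiratory infection applies only at the screening visit, so off-season use of a cold remedy later on is possible but undocumented.

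**4. Visit 6.** Rescue antihistamines and nasal corticosteroids are supplied from about two weeks before the May season and throughout it. Appendix 8 sets 5 and 14 days for these classes but does not name Visit 6. SAP 7.2.1 lists the 6-month comparison of the arms among those of interest, so these data are used.

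**The case against.** The best case against the point is that it concerns one irregular cell in an untidy table. The theophylline heading, for instance, shows 14 days above sub-rows of 24 hours and 2 days. A typing slip or a fault in reading the PDF is as plausible as a deliberate rule. This is fair, and it is why the source cell should be checked. It does not remove the defect, because any value that begins with a 3 and a decimal point is below 5, and as printed the row is the operating rule.

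An investigator might also apply both rows to a combination product and use the longer, since the antihistamine row is not limited to single-agent products. That reading is open, but the more specific row would normally govern.

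On 6.4.8.1, the words about nasal challenges could be taken to include Visit 6. The bracket that follows lists visits and leaves it out, so the text needs settling.

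The objection on size largely stands. The covered challenges are off-season, the same rule binds both blinded arms, and a blunted score at screening would tend to fail the entry cut-off, which affects recruitment more than the randomised comparison. The remark in Protocol 6.5.9 is about relieving skin-test symptoms and says nothing about residual effect 3 to 5 days after stopping.

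A reader might infer that the row reaches most of the challenges in the blinded phase. It does not: screening and V0b both precede the first dose.

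**Conclusion.** The combination row is wrong as written, by 2 days against the plan's own antihistamine interval. The error is minor. It rests on the printed table alone, subject to a check of the source PDF, and on the premise that a combination product needs the longer of its components' washouts. The wrong appendix number and the missing challenge visits are confirmed by direct comparison.

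A reader might go further and infer that the primary result is biased or that power is lost. The documents do not support this. They give neither the frequency of combination-product use nor the residual effect of an antihistamine 3 to 5 days after the last dose, so any figure for lost effect or power would rest on assumption. Nor does the point require a new exclusion from the per-protocol sample. That would select on behaviour after randomisation and is not needed to correct a table.

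**What to change.** Three edits to the protocol, made together:

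1. In Appendix 8, set the antihistamine-decongestant row to 5 days, after checking the cell in the source PDF.
2. In 6.4.8.1, change the reference from Appendix 7 to Appendix 8.
3. In the Appendix 8 heading and the 6.4.8.1 bracket, name every visit with a nasal challenge: add Visit 6, and add Visits 8 and 9, which repeat the Visit 7 procedures. Keep Visit 5, which is listed for its biopsy.

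The cost is one table cell, one cross-reference and a few visit numbers. Anyone using a combination product stops it 2 days earlier. Naming Visit 6 may mean booking some participants later within July to October, so that the 14 days for nasal corticosteroids can pass. Sample size, analysis sets and data collection do not change.

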Appendix 9: Daily Diary Card

- Please answer the following questions once daily
- Mark an X in case of YES
- Leave the field empty in case you answer the question with NO
- If you have not taken the tablet please specify the reason on why you have not taken the tablet in the comment field

January 2014						
Day	Did you take the tablet?	Comment	Did you feel any Itchiness in the mouth after the treatment?	Did you feel any swelling under the tongue after the treatment?	Did you experience any other symptoms? (please specify)	Where these symptoms bothersome?
1.						
2.						
3.						
4.						
5.						
6.						
7.						
8.						
9.						
10.						
11.						
12.						
13.						
14.						
15.						
16.						
17.						
18.						
19.						
20.						
21.						
22.						
23.						
24.						
25.						
26.						
27.						
28.						
29.						
30.						
31.						

etc.

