6.7.2 Grading of adverse events/adverse reactions

The study site will grade the severity of AEs/ARs for the study medication according to the following criteria:

- All local reactions not associated with systemic signs or symptoms will be graded according to Table 6.
- All systemic reactions to AIT will be graded according to the WAO SCIT Reaction Grading System³⁵. The following modification will apply for AIT: Under Grade 1 (Symptoms/signs of 1 organ system present), “throat clearing (itchy throat)” is not considered a systemic reaction.

Table 6: Sublingual immunotherapy (local reactions) Grade Description²⁹

Symptom/sign (see Table I)	Grade 1: Mild	Grade 2: Moderate	Grade 3: Severe	Unknown severity
Pruritus/swelling of mouth, tongue, or lip; throat irritation, nausea, abdominal pain, vomiting, diarrhea, heartburn, or uvular edema	
 Not troublesome AND No symptomatic treatment required AND No discontinuation of SLIT because of local side effects 	
 Troublesome OR Requires symptomatic treatment AND No discontinuation of SLIT because of local side effects 	
 Grade 2 AND SLIT discontinued because of local side effects 	Treatment is discontinued, but there is no subjective, objective, or both description of severity from the patient/physician.

Each local AE can be early (<30 minutes) or delayed.

The study site will grade the severity of AEs/ARs for the following selected study procedures according to the following criteria:

- All local reactions to nasal biopsy will be recorded according to Table 7.
- All local reactions to allergen skin testing that are to be reported as AEs and are not associated with systemic signs or symptoms will be graded according to Table 8.
- Although very unlikely, systemic reactions related to either AIT tablet treatment, nasal challenge or intradermal or skin prick test procedures will be graded according to the WAO SCIT Systemic Reaction Grading System³⁵.

Table 7: Nasal biopsy procedure (local reactions)

Grade Description

1 Bleeding that does not respond to finger pressure, pain that does not respond to paracetamol, or symptoms which require a telephone consultation with a study physician.

2 Bleeding or pain that requires a visit to the doctor for treatment.

3 Bleeding or pain that requires hospitalization.

Table 8: Intradermal and skin prick test procedure (local reactions)

Grade Description

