2. Mini Rhinoconjunctivitis Quality-of-Life Questionnaire (miniRQLQ) scores will be collected weekly during the pollen season (Appendix 3 of protocol). The mean composite score in each treatment group during the peak pollen season (beginning of May to end of July) will be compared. Furthermore the maximum RQLQ will be compared.
Mini RQLQ will also be recorded pre- and post-season. Adding the scores of the 14 questions to form a single score per measurement will form the score of the mini RQLQ. The Inform database team will perform this.
3. Symptoms and severity of symptoms after intake of the daily tablets will be recorded on a daily questionnaire (Appendix 9 of protocol), which the participants will fill out at home. The type of symptom (itchy mouth, swelling of the mouth or other) and the WAO Grade of the local symptoms will be calculated daily and active will be compared. The duration of the symptoms in days and the duration of symptoms in minutes will be specified, the AIT trial team according to the records assessed on the paper CRF on every visit will give this information.
4. Global Evaluation Score 3 (Visual Analogue Scale of overall Hayfever symptoms in the last week) (Appendix 4 of protocol) will be collected weekly during the pollen season. The mean composite score in each treatment group during the peak pollen season (beginning of May to end of July) will be compared. Furthermore the maximum Global Evaluation Score 3 will be compared between the placebo and the active treatment group.
5. The total nasal symptoms score (TNSS) measured at 0, 5, 15, 30 and 60 minutes (Early phase response (EPR)) following grass pollen nasal allergen challenge at baseline, at 6 and at 12 months (Appendix 6) will be assessed similar to the primary endpoint.

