8.2 Adverse Events

Side effects to the treatment will be recorded daily according to the WAO guidelines. They will be recorded as an Adverse Event (AE) only when the severity of the symptoms has a > Grade 1 according to WAO guidelines.

All AEs will be classified using the National Cancer Institute's (NCI's) Common Toxicity Criteria for Adverse Events (CTCAE). This will be performed by the AIT study team. Each AE is entered on the case report form (CRF) once at the highest severity and the duration of the AE will be recorded. Also information about System Organ Class – Term and CTCAE Term – Term will be included.

CTCAE classification version 4.03: http://evs.nci.nih.gov/ftp1/CTCAE/CTCAE_4.03_2010-06-14_QuickReference_8.5x11.pdf will be used by the AIT team and send to the Inform database via excel files.

An overall summary table will be developed to report the number of events and the number and percentage of subjects having at least one event in the following categories:

- AEs
- AEs indicated as serious
- AEs that lead to study drug discontinuation
- AEs with an outcome of death
- AEs that were reported as being related to a study drug
- AEs reported by maximum severity

Exploratory analysis will be carried out for the different type of adverse events to compare the intervention with control group: frequency tables, bar graphs, summary statistics.

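### The daily side-effect diary cannot tell No from missing and has no treatment field, so the SAP's daily local-reaction rates and grades are not fully determined by it

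*Protocol*

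**What the plan says.** Participants complete one row per day on the card in Protocol Appendix 9. They mark an X for Yes; for No the instruction is "Leave the field empty in case you answer the question with NO". Each row asks "Did you take the tablet", then about itch, swelling and other symptoms, and ends with one severity item, "Where these symptoms bothersome", shared by all symptoms. On a day without a tablet the card asks for an explanation: "If you have not taken the tablet please specify the reason on why you have not taken the tablet in the comment field". No column asks whether a symptom was treated.

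SAP 7.3.1 item 3 takes symptom type and severity from this card and says that "the WAO Grade of the local symptoms will be calculated daily", for comparison between arms. Symptom duration comes from a different source, the paper CRF completed at visits.

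On grading, Protocol 6.7.2 says: "All local reactions not associated with systemic signs or symptoms will be graded according to Table 6". In that table a reaction is Grade 1 only if it is neither troublesome nor treated and the tablet is continued. It is Grade 2 if it is troublesome or treated, with the tablet continued. SAP 8.2 says of treatment side effects: "They will be recorded as an Adverse Event (AE) only when the severity of the symptoms has a > Grade 1". Protocol 6.7.1.2 sets a different threshold for the expected mouth symptoms: they go unreported as long as they are not bothersome, and treatment plays no part in that rule. SAP 8.1 rules out imputing missing safety data.

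**The concern.** Two things the SAP needs cannot be read from the card.

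The first is which days were observed. The SAP 8.1 rule on missing safety data can be applied only where missing data can be recognised. On this card a skipped row carries no mark, and neither does a row of true No answers on a day without a tablet if the reason was left out. Compliance under SAP 6.2 comes from the pharmacy count, which gives a total and does not show which days were missed.

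The second is the grade. Table 6 turns on two facts, whether the reaction was troublesome and whether it was treated, and the card records only one of them.

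At stake is secondary objective 3 in Protocol 5.2, the presence and severity of side effects. Protocol 6.4.1 expects local mouth reactions in 50% to 60% of those treated, so the card carries the main expected tolerability signal.

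**Working it through.** The documents give no figure for diary completion or daily symptom frequency, so there is no stated result to reproduce. Three checks follow. All skip and symptom rates are assumptions.

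**1. Grade logic.** This reads bothersome on the card as troublesome in Table 6, takes Table 6 as the local grade that the SAP means, and supposes that the tablet is not discontinued.

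| Troublesome | Treated | Table 6 | Card alone | Above Grade 1: Table 6 / card |
|---|---|---|---|---|
| No | No | 1 | 1 | No / No |
| No | Yes | 2 | 1 | Yes / No |
| Yes | No | 2 | 2 | Yes / Yes |
| Yes | Yes | 2 | 2 | Yes / Yes |

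The card alone gets three of the four combinations right. The one it misses crosses the SAP 8.2 threshold.

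**2. Daily rate if blank rows stay in the denominator.** Let p be the true share of days with symptoms and s the share of days left blank, with blanks unrelated to symptoms. Then observed rate = p × (1 − s). Assume p = 30% active and 5% placebo, a true difference of 25 points and a ratio of 6.0.

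| s, both arms | Active | Placebo | Difference | Ratio |
|---|---|---|---|---|
| 5% | 28.5% | 4.75% | 23.75 | 6.0 |
| 10% | 27.0% | 4.5% | 22.5 | 6.0 |
| 25% | 22.5% | 3.75% | 18.75 | 6.0 |

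With equal skipping, the rates and their difference shrink by the share s and the ratio does not change. With assumed rates of 10% and 2%, s = 25% gives 7.5% and 1.5%, a difference of 6 points instead of 8.

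Unequal skipping, using 30% and 5% again:

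- Active 10% blank, placebo 25%: 0.30 × 0.90 = 27.0% and 0.05 × 0.75 = 3.75%. The ratio is 7.2 and the difference 23.25 points.
- Active 25% blank, placebo 10%: 0.30 × 0.75 = 22.5% and 0.05 × 0.90 = 4.5%. The ratio is 5.0 and the difference 18.0 points.

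So the ratio can rise or fall. The absolute difference usually falls. It widens only if (placebo p × placebo s) exceeds (active p × active s), which at these rates means an active blank share below one sixth of the placebo share.

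**3. Participants ever affected.** A participant with k symptomatic days is still counted with probability 1 − s^k, if days are skipped independently. At s = 25%:

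- k = 1: 75%
- k = 2: 93.8%
- k = 5: 99.9%
- k = 10: above 99.99%

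Counts of participants with any symptom are therefore robust unless symptoms last only a day or two.

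**The case against.** A reader might infer that skipped days and days without a tablet are counted as symptom-free, and that AIT side effects are therefore understated. The documents do not support that.

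- Neither document says that a blank or no-tablet day enters as a negative day. The denominator is undefined, which is a gap and not a stated miscoding.
- The card already separates most cases. A tablet X shows that the row was used, and a blank tablet box with a written reason shows a day without a tablet. On such a day, No is the true answer to the itch and swelling items, which ask about symptoms after the dose. Only wholly blank rows without a reason, and single overlooked items, remain ambiguous.
- The direction of bias in the comparison is not established. Both arms use the same card, every rate above is assumed, and the ratio can move either way. The 75% compliance criterion for the per-protocol sample concerns tablets counted by pharmacy and says nothing about diary completion.
- Adverse events are also collected by observation, questioning and spontaneous report (Protocol 6.7.6.1). The SAP schedule lists adverse events and concomitant medications across the visits, and nothing says that the grade uses the card alone.

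All of this stands, and it limits the point without removing it. The visit records are not linked by day to the card. The SAP names the visit CRF for duration, not for treatment. Antihistamines are also supplied as hay-fever rescue medication through the season (Protocol 6.4.8.1), so an entry for one does not by itself show that it treated a mouth reaction.

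**Conclusion.** The point holds in a limited form. On the face of the documents, the card cannot distinguish No from missing for blank rows and unanswered items, and it lacks one of the two inputs that Table 6 needs. Daily rates may be understated, by the share of blank days, if those rows stay in the denominator. Under the assumed 5% to 25% blank, that is a relative loss of 5% to 25%. If participants skip more often on symptomatic days, the loss is larger. The effect on the comparison between arms depends on differential skipping, which is unknown.

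The misgrading is confined to reactions that were treated but not marked bothersome. Such a reaction could fall below the SAP 8.2 threshold unless visit questioning or the medication record brings it up. How often this happens cannot be estimated from the documents.

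The reach is modest: an exploratory daily analysis and part of the safety tabulation. Counts of participants ever affected are little changed unless symptoms are brief, and the primary endpoint is unaffected. The change is worth making because it is cheap and most of it can be applied to cards already collected.

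**What to change.** **Card.** Replace mark-or-blank with explicit Yes/No boxes, and add a field asking whether medicine was taken for the symptom.

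**SAP 7.3.1 item 3.**

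- Use as denominator the days on which the tablet box is marked.
- Treat rows with no entry as missing, and report their number by arm.
- Name the visit CRF or the concomitant-medication record as the source of symptomatic treatment for cards already collected.
- State that the local grade is the one in Table 6, if that is what is meant.

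**Reporting threshold.** Reconcile Protocol 6.7.1.2, which rests on bothersome alone, with SAP 8.2, which rests on a grade above 1 and so, through Table 6, also takes in treated reactions.

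**Cost.** A form edit and a few SAP sentences, a slightly longer card and fewer evaluable days. On existing cards, a symptom item overlooked on a tablet-marked day will still be read as No; the denominator rule cannot repair that.
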